1.2 Summary

Some patients continue to suffer physical or psychological impairments weeks and months after infection with severe acute respiratory syndrome coronavirus 2 (SARS-CoV-2). Shortness of breath is one of the most frequently observed symptoms (15-61%), either singly or in combination (1, 2). When treating patients with dyspnoea, conventional diagnostic tools (computed tomography, spirometry, body plethysmography) often fail to detect pathological changes, making it difficult for the treating physician to choose an appropriate therapeutic approach (3-6). Therefore, it would be desirable to have an examination procedure that reveals the pulmonary changes in post-Covid patients that are hidden from other diagnostic procedures.

Electrical impedance tomography (EIT) is a non-invasive and radiation-free imaging technique that can show regional ventilation of the lungs almost "in real time" based on changes in the electrical impedance of the thorax during inspiration and expiration. This method is based on the observation that the electrical conductivities of biological tissues differ significantly depending on their nature and functional state. Clinical questions in which the inhomogeneity of lung ventilation is to be analysed (e.g. under- or overinflation of individual lung areas, lung collapse, etc.) can be investigated particularly well with EIT, since intrathoracic impedance changes correlate strongly with changes in regional lung ventilation (7, 8).

So far, EIT has mainly been used as a monitoring method in intensive care medicine to adapt ventilation settings and other therapeutic measures individually to the needs of the patient. In this field, the method has proven useful to get an overview of the distribution of a respiratory volume in a transverse EIT layer, to compare different lung regions, to identify inhomogeneities and to evaluate regional ventilation during spontaneous breathing.

1.3 Synopsis

Title of the study	Visualisation of changes in regional ventilation in dyspnoeic post-COVID patients - a case-control study using electrical impedance tomography
Acronym	ViReVentPoCov
Director of Studies	Dr. med. [name]
Deputy of the Director of Studies	Priv.-Doz. Dr. med. habil. Dr. [name]
Indication/target population/disease	Post-COVID patients and reference group of lung-healthy subjects
Study design/methodology	
 - monocentric - not controlled; type and number of control groups: 1 - Case-control study (retrospective patient data from routine treatment vs. reference group)
Aims of the clinical trial/objectives	
Primary objective: Examine whether post-COVID patients with dyspnoea show changes in regional ventilation compared to a reference group of lung-healthy subjects.
 
Secondary objectives: To review the indication of EIT in post-COVID patients with dyspnoea.

Study objective	
Primary target figure/main target criterion: There is a difference in regional ventilation between healthy lung patients and post-COVID patients with dyspnoea.
 
Changes in the configuration of the minute image and the regional ventilation delay (RVD) image, the RVD diagram and video-based analysis of the dynamic images
 
Secondary target variables/ secondary target criteria: Review of the indication for an EIT examination in patients with post-COVID syndrome

Number of patients	
Number in analysis: n=20 post-COVID patients / n=80 healthy lung patients
 
Considering the first comparison of EIT data of post-COVID patients with those of a reference group, no formal calculation of the number of patients is calculated and a patient number of n=20 and a subject number of n=80 are assumed to be sufficient. The number of subjects is planned to be higher than the number of patients so that enough reference values of EIT in the different age groups can be analysed and compared with those of the patients in the age-adjusted comparison.

Inclusion criteria	EIT data of post-COVID patients with dyspnoea from the post-COVID outpatient clinic of university hospital Jena (retrospective) and lung-healthy non-smokers without resting or exertional dyspnoea (both groups breathing spontaneously).
Exclusion criteria	
 - Pacemaker - BMI over 50, here the PulmoVista® 500 system should not be used according to the manufacturer. - uncontrolled body movements
Timetable (duration of study)	
patient-related:
 
Duration of study-related measures: 10 min. EIT examination
 
Follow-up period: None
 
study-related:
 
Start (time): After ethics vote
 
Recruitment period: approx. 1 week
 
Total duration: approx. 2 weeks
 
expected completion including evaluation (date): 15.06.2022
 
End of study: after inclusion of n=20 subjects in the reference group and evaluation of the EIT data of the post-COVID patients ten

1.4 Flowchart

*Parameters of regional ventilation from the EIT examination
(areated regions, distribution of ventilation, non-ventilated areas, minute images, dynamic images, regional ventilation delay (RVD), pendulum air)*

1.5 Visit plan

Table or list with visits and the (study-specific) events that take place, e.g. examinations and measures

Medical history/baseline data collection	+					
Informed consent	+					
Inclusion and exclusion criteria	+					
Randomisation	-					
physical examination	-					
Recording of concomitant medication	+					
Sampling for laboratory ¹	-					
Recording of adverse events	+					

1. Question or background

- conventional diagnostic tools (computed tomography, spirometry, body plethysmography) often fail to detect pathological changes in post-COVID patients with dyspnoea, which makes it difficult for the treating physician to choose an appropriate therapeutic approach
- Post-COVID patients who underwent electroimpedance tomography as part of routine diagnostics have shown clear abnormalities.
- Up to now, there are no reference data from electroimpedance tomography (created regions, distribution of ventilation, non-ventilated areas, minute images, dynamic images, video-based analysis of dynamic images, regional ventilation delay, pendulum air) in spontaneously breathing lung patients, but only EIT data from ventilated patients and non-invasively ventilated subjects. Thus, a reference group is missing.

1.1 Initial situation

1.2 Question and justification of the project

This study aims to answer the following question:

Do spontaneously breathing post-COVID patients have changes in their regional ventilation that cannot be detected in lung-healthy subjects?

2.3 Justification of the treatment and examination procedures

Electroimpedance tomography (EIT) is a non-invasive, radiation-free imaging examination procedure based on the measurement of impedance changes. EIT can be used to visualise regional ventilation based on the electrical conductivity of the thorax at the bedside. This method therefore provides valuable information about the regional ventilation of the lungs.

3. Study objectives

- Aims of the study:
Visualisation of regional ventilation disorders in post-COVID patients compared to a reference group.
- The study will investigate whether there are significant differences between regional ventilation (created regions, distribution of ventilation, non-ventilated areas, minute images, dynamic images, video-based analysis of dynamic images, regional ventilation delay, pendulum air) in post-COVID patients compared to a reference group of lung-healthy subjects.

3.1 Primary study objective and primary endpoint

- Main question:
Are there significant differences between regional ventilation in post-COVID patients compared to a reference group?
- primary endpoint (target variables):
Relative distribution of the respiratory volume across the so-called regions of interest (ROIs). adjustable in size and arrangement, in which the ventilation ratios represented by the EITcan be measured (regional ventilation of the lung (regional ventilation of the lung: created regions, distribution of ventilation, non ventilated areas, minute images, dynamic images, video-based analysis of dynamic images, regional ventilation delay, pendulum air)

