10.1 Patient identification list

All patient-related data is recorded in pseudonymised form. For this purpose, a non-speaking pseudonym is used, from which alone the identity of the patient cannot be inferred. In order to obtain unique patient identification numbers, a combination of a fixed trial centre number and a consecutive centre-specific patient number is chosen.

The trial centre maintains a patient identification list in which the patient identification numbers are linked to the full patient names of the participants, patient identification number and date of birth, if applicable. This list serves the possibility of later identification of participating persons. It will be kept absolutely confidential and will not leave the trial centre. It will be archived for **at least ten years** after the end of the study.

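### The primary endpoint rests partly on image and video reading and on adjustable ROIs, but the plan specifies neither masking to group nor a common ROI layout, so evaluator expectation could bias it

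*Combined protocol and SAP*

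**What the plan says.** - **Endpoint, section 3.1.** The primary endpoint is the relative distribution of breath volume over ROIs described as "adjustable in size and arrangement, in which the ventilation ratios represented by the EITcan be measured". The same sentence lists further components, among them "video-based analysis of dynamic images, regional ventilation delay, pendulum air". It gives no ROI layout and no scoring rule.
- **Synopsis, section 1.3.** Under the main target criterion stands "Changes in the configuration of the minute image and the regional ventilation delay (RVD) image, the RVD diagram and video-based analysis of the dynamic images".
- **Expectation, section 1 (Question or background, printed after the visit plan).** "Post-COVID patients who underwent electroimpedance tomography as part of routine diagnostics have shown clear abnormalities".
- **Test, section 9.4.** A Wilcoxon rank sum test is named for two quantities: the 32x32 pixel matrices of the tidal images and the ROI distribution. No method is given for the image or video readings.
- **Data sources, sections 4.5, 4.6 and 7.** The 20 patient recordings are retrospective, from routine care. The 80 reference recordings are to be made on staff and students, with inclusion planned for June to September 2022.
- **Pseudonyms, section 10.1.** "a non-speaking pseudonym is used, from which alone the identity of the patient cannot be inferred", and "a combination of a fixed trial centre number and a consecutive centre-specific patient number is chosen".
- **Quality control, section 5.** The only measure described for the examination is automatic calibration of the device.

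Masking, an independent evaluation, a reading order and a reading manual are not mentioned anywhere in the document.

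**The concern.** In a two-group comparison, an evaluator who knows the group and expects one group to look abnormal can move the result in that direction. This can happen in the grading of an image or video, or in where an ROI is placed. Such a shift acts between the groups, so it cannot be told apart from a true difference in the results, and a larger sample does not reduce it. Here the expectation is written into the background section, and the components most open to judgement are part of the primary endpoint. The plan's only coding measure is directed at confidentiality. At stake is whether a positive finding on ROI shares, or on image and video patterns, can be credited to the patients' lungs.

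**Working it through.** **Step 1. Which components depend on an evaluator?**

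| Component | Planned test (9.4) | Route for expectation |
|---|---|---|
| 32x32 pixel matrices | Wilcoxon | Little: ROI placement does not define them |
| ROI shares | Wilcoxon | Open if ROIs are set with knowledge of group, since 3.1 leaves them adjustable and fixes no layout |
| Minute and dynamic images, video analysis, and regional ventilation delay and pendulum air where judged by eye | None stated | Open: no scoring rule and no masking specified |

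**Step 2. Could group be known to the evaluator?** Section 10.1 says only that identity cannot be inferred from the pseudonym; it does not mention group. The numbers are consecutive within the centre. One group consists of existing recordings and the other is newly recorded, so number or recording date could separate them. Whether they do depends on how numbers are assigned and what the evaluator sees, which the plan does not say.

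**Step 3. How large could the effect on the ROI test be?** The plan gives no alpha, power, effect size or SD, so it has no figure to reproduce. What follows is an illustration for ROI shares only.

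- From the documents: n = 20 and n = 80 (section 4.4).
- Assumed: two-sided alpha 0.05, normally distributed data, no true difference, and an evaluator-induced offset of b SD in one group.

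Standard error of the difference: sqrt(1/20 + 1/80) = sqrt(0.0625) = 0.25 SD.

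False-positive rate = Φ(b/0.25 − 1.96) + Φ(−b/0.25 − 1.96).

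For b = 0.2: b/0.25 = 0.8, so Φ(−1.16) + Φ(−2.76) = 0.123 + 0.003 = 0.126.

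The Wilcoxon column comes from 10,000 simulated tests per row.

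| Assumed offset b (SD) | b/0.25 | Normal formula | Wilcoxon simulation |
|---|---|---|---|
| 0 | 0 | 0.050 | 0.048 |
| 0.1 | 0.4 | 0.069 | 0.063 |
| 0.2 | 0.8 | 0.126 | 0.119 |
| 0.3 | 1.2 | 0.224 | 0.208 |
| 0.5 | 2.0 | 0.516 | 0.484 |

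**Step 4. Scale.** Under the same assumptions, 80% power at 20 versus 80 needs a true difference of (1.960 + 0.842) × 0.25 = 0.70 SD, or about 0.72 SD for the Wilcoxon test. An offset of 0.2 SD is thus more than a quarter of that difference (0.2/0.70 = 0.29).

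**The case against.** The best defence is that both quantities with a planned test are numeric, that one common ROI layout would fit section 3.1 equally well, and that this is a first comparison. Much of this stands, and it limits the point. Several stronger readings are tempting and are not supported:

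- **That the recordings are read unmasked.** The plan is silent. It specifies no masking, which is not a statement that there is none.
- **That an evaluator sets ROIs for each recording.** Describing ROIs as "regions of interest (ROIs). adjustable in size and arrangement" states a property of the method, not who adjusts them or when.
- **That the examiner listed in section 5 reads the images.** The qualification given there concerns recording technique. No section says who evaluates.
- **That the pseudonyms do reveal the group.** Section 10.1 does not say that both groups share one number series or that evaluators see number or date. It shows only that group is not protected.
- **That the false-positive figures apply to the whole endpoint.** The pixel comparison is largely unaffected. The image and video readings have no planned test whose error rate could be raised.
- **That the bias could never be undone.** As long as recordings are kept, a fixed layout or a masked re-reading can be applied later.

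It is also fair to say that a fixed ROI layout alone would close the route into the tested ROI shares. It would not protect the image and video readings. Those have no planned test, but both 3.1 and the synopsis place them in the primary endpoint, so masking still matters there.

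**Conclusion.** The point holds as a gap in the plan. Nothing in it protects the evaluator-dependent parts of the primary endpoint from knowledge of group, and the plan states the expected direction beforehand. The image and video readings are the most exposed. The Wilcoxon comparison of ROI shares is exposed only if ROIs are set with knowledge of group.

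In that case, an offset of 0.1 SD would do little (about 6-7% false positives against a nominal 5%), while 0.2, 0.3 and 0.5 SD would give about 12%, 21% and 48%. The offsets and the alpha are assumptions, and the documents give no measure of evaluator variability, so the true size is unknown. The change should be made before evaluation, but the gap does not invalidate the study, since the pixel comparison is largely untouched.

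**What to change.** - **Sections 3.1 and 9.4:** define one ROI layout in advance and apply it identically to all 100 recordings (20 + 80).
- **Section 9.4:** add short written scoring criteria for the image and video readings, and state that recordings are evaluated in random order by evaluators masked to group.
- **Section 10.1:** export the recordings under random, non-consecutive codes with name, date and group removed. Have an existing team member who does not read images hold the code list until the readings are locked.

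The cost is some file recoding, a short scoring rule and a few sentences of text. No extra reader or examination is needed. If the evaluator also recorded the volunteers, masking may be imperfect; the report should then say so. If no evaluator-induced offset remains, the illustrative false-positive rate returns to about 5%.

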3.2 Secondary study objectives and secondary endpoints

- Side issues: none
- No secondary objective criteria

4. study design and description

4.1 Nature of the study

This is a case-control study

4.2 Type of therapy assignment

none

4.3 Number and type of comparison groups

A reference group is formed (up to now there are no published data on the target values of spontaneously breathing lung patients mentioned under 3.1).

4.4 Scope of the study

n=20 post-COVID patients, n=80 lung healthy volunteers

4.5 Patient recruitment

- Accessibility of the intended number of patients:
- Given by retrospective analysis of EIT data of post-COVID patients from the UKJ outpatient clinic (planned n=20).
- Number of participants: n=80 subjects
- Procedure for recruiting examination candidates: Addressing UKJ staff/students

4.6 Schedule

The expected total study duration is 3 months.

- Duration of the study in the individual patient: 10 minutes
- No interim evaluation planned
- End of study (end of study): after inclusion of n=80 patients in the reference group.
- If necessary, define times at which checks are carried out,
 - whether recruitment is proper: one week after the start of the study
 - Whether patient safety is ensured: not applicable, as radiation-free non-invasive procedure without known side effects.
 - whether the data quality is sufficient: before each EIT measurement by automatic calibration of the device
- possible representation of some milestones over time (indicate month/year):
 - Inclusion of first patient/proband (FPFV) June 2022
 - Inclusion of last patient/proband September 2022
 - End of study of the last patient (LPLV) -
 - Closing the database: after reaching n=80 subjects
 - End of statistical evaluation: September 2022
 - Final report: September 2022

5. required equipment

- Existing equipment and furnishings:
2 EIT units, single examination room in the ZNA.
- required qualifications or experience of the examiners:
Doctor; trained in EIT derivation technique
- Minimum number of subjects and patients to be included:
n=20 subjects undergoing EIT examination;
n=20 patients from the post-COVID outpatient clinic in whom the examination was performed as part of routine examinations (retrospective evaluation).
- Participating examiners: Dr. [name]
- an evaluation and initiation visit can be dispensed with, because the method is used in the routine
- study-specific quality requirements for diagnostic measures:
The quality of the EIT derivation is ensured by automatic calibration at the beginning of each examination. If the calibration is not passed, the examination is not possible.

5.1 Conditions for participation in the study

Only adult participants who give written informed consent to participate (subjects) will be included in the study.

Lung-healthy subjects (reference group): Non-smokers, no resting or exertional dyspnoea

Post-COVID patients: presentation at the post-COVID outpatient clinic of the UKJ with subsequent EIT examination (retrospective evaluation of EIT data collected during routine diagnostics).

6. selection of patients

- *Main selection criterion: patients with a post-COVID syndrome who presented at the post-COVID outpatient clinic and lung-healthy subjects who do not smoke.
(retrospective analysis of EIT data of post-COVID patients examined in the post-COVID outpatient clinic of the UKJ and EIT examination of lung-healthy spontaneously breathing subjects from whose EIT data a reference group is to be formed, which does not yet exist).*
- *Female and male patients can be included.*

6.1 Inclusion criteria

- *Reference group: no resting or exertional dyspnoea, non-smokers*
- *Post-COVID patients: EIT examination performed as part of routine presentation at the post-COVID outpatient clinic.*

6.2 Exclusion criteria

- Pacemaker wearers
- BMI over 50, here the PulmoVista® 500 system should not be used according to the manufacturer
- uncontrolled body movements

7. Process of the study

- Recruitment of lung-healthy subjects (UKJ staff/students)
- Formation of the reference group: for each subject, conduct an EIT examination in a quiet and distraction-free environment (single room ZNA) to avoid artefacts.
- Post-COVID patients: retrospective analysis of EIT data
- Comparison of the EIT parameters of the two groups

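### The planned rank sum test compares clinic patients with hospital staff and students without using BMI or sex, so an imbalance in either could contribute to, or hide, a group difference in ROI shares or pixels

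*Combined protocol and SAP*

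**What the plan says.** **Source of the groups.** Section 4.4 sets the numbers: "n=20 post-COVID patients, n=80 lung healthy volunteers". Section 6.1 defines the cases: "Post-COVID patients: EIT examination performed as part of routine presentation at the post-COVID outpatient clinic". Section 4.5 recruits the volunteers from a different population: "Procedure for recruiting examination candidates: Addressing UKJ staff/students". Section 7 repeats this. Their only stated criteria in 6.1 are: "Reference group: no resting or exertional dyspnoea, non-smokers".

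**BMI and sex.** BMI appears only in the exclusion criteria (Synopsis and 6.2): "BMI over 50, here the PulmoVista® 500 system should not be used according to the manufacturer". The limit is not tied to one group. Sex appears only in section 6: "Female and male patients can be included". No section matches, stratifies, sets quotas or adjusts for either.

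**Analysis.** Section 9.4 is a single sentence. It applies the Wilcoxon rank sum test to the 32x32 pixel matrices and to the ROI shares. The Synopsis and 9.3 mention an age-adjusted comparison, but 9.4 does not say how it is done.

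**Measurement.** Section 1.2 says that EIT relies on impedance changes of the thorax and that "the electrical conductivities of biological tissues differ significantly depending on their nature and functional state". Section 3.1 makes the relative distribution of breath volume across ROIs the primary endpoint, and describes the ROIs as adjustable in size and arrangement.

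**The concern.** The groups are not randomised and come from different sources, so they may differ in more than post-COVID status. A rank sum test attributes any systematic shift between them to group membership. BMI and sex are obvious candidates for imbalance. By the protocol's own account the signal passes through the tissues of the thorax, and comparing pixel by pixel presumes that a given pixel represents the same anatomical place in everyone. Adjusting for age would remove a BMI or sex imbalance only to the extent that it follows age.

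The primary question is whether patients differ from the reference group. If BMI or sex both differs between the groups and affects the endpoint, a positive result may partly reflect body build, and a null result may hide a real difference.

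**Working it through.** **Is there a figure of the plan's own to reproduce?** No. The plan states no alpha, power, effect size or SD, and the Synopsis says that no formal sample size calculation was made. A two-sided 0.05 level is assumed below.

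**Inputs from the documents:** 20 patients, 80 volunteers, Wilcoxon rank sum test, no covariates.

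**Inputs assumed:** the BMI gap between groups, *d*, in SD units; the within-group correlation of BMI with one ROI share, *ρ*; a linear relation; no true lung difference.

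**Model.** share = ρ × BMI + √(1 − ρ²) × noise, so the within-group SD is 1 and the spurious shift between groups is δ = ρ × d.

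**Approximate rejection rate.** The standard error of the group difference is √(1/20 + 1/80) = 0.25 SD. With the rank sum efficiency factor √(3/π) = 0.977, the standardised shift is λ = 0.977 × ρd / 0.25, and the rejection rate is Φ(λ − 1.96) + Φ(−λ − 1.96).

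- d = 0.5, ρ = 0.2: δ = 0.10, λ = 0.39, rate 6.8%
- d = 0.8, ρ = 0.3: δ = 0.24, λ = 0.94, rate 15.5%
- d = 0.8, ρ = 0.5: δ = 0.40, λ = 1.56, rate 34.6%
- d = 1.0, ρ = 0.5: δ = 0.50, λ = 1.95, rate 49.8%

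**Simulation of the planned test** (4000 replicates per scenario) agrees:

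| BMI gap | ρ = 0.2 | ρ = 0.3 | ρ = 0.5 |
|---|---|---|---|
| 0 | 5.2% | 5.0% | 5.2% |
| 0.5 SD | 7.3% | 9.4% | 15.5% |
| 1.0 SD | 11.7% | 20.7% | 49.2% |

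A separate run gave 6.1% to 15.4% at a 0.5 SD gap, 9.7% to 34.2% at 0.8 SD and 13.2% to 50.1% at 1.0 SD, for correlations 0.2 to 0.5. With *ρ* = 0 and gaps up to 1.0 SD, the rate stays at about 5%.

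**Sex, also on assumed values.** With an effect of 0.5 SD, the rate is 5.8% for 70% v 50% female and 9.2% for 40% v 70%. With an effect of 1.0 SD, it is 11.4% and 19.8%.

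**Masking.** With 20 v 80, the planned test has about 78% simulated power for a true difference of 0.72 SD when BMI is irrelevant. If a 0.8 SD BMI gap works in the opposite direction, simulated power falls to 44%, 35% and 23% at *ρ* = 0.3, 0.4 and 0.5. The net shift at *ρ* = 0.5 is 0.72 − 0.40 = 0.32 SD, for which the formula gives 24%.

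**With adjustment.** A linear model with group and the covariate kept the false-positive rate at 4.3% to 5.6% in every BMI and sex scenario. Rank regression on group, age, BMI and sex gave about 4% to 6%, and kept 74% to 83% power in the masking scenarios.

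**The case against.** The documents never say that BMI or sex changes EIT values. The conductivity statement in 1.2 explains how EIT images ventilation and does not address differences between people. The BMI limit is reported as manufacturer's advice without a reason; it supports not using the device above 50, not a graded bias below it. No BMI or sex distribution is given for either group. Every simulated rate therefore depends on assumed inputs, and any covariate given a gap and a correlation would produce similar figures. At the low end the rate is close to nominal. The simulation also leaves out the intended age adjustment. All of this stands, and it limits the point to what could happen.

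A reader might infer more from the plan in three ways, none of which the documents support:

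- *That patients are heavier than the volunteers.* The limit of 50 covers both groups, and hospital staff may span a wide BMI range.
- *That the primary endpoint is read at a fixed anatomical place.* That describes the 32x32 matrix. The ROIs are adjustable, although no rule for setting them is given. The endpoint is also a relative share, which may cancel pure scaling by body size, though not effects of shape or position.
- *That BMI and sex are already recorded, so the change is wording only.* The visit plan (1.5) lists baseline data without saying what they contain and plans no physical examination.

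Nor is the exclusion criterion itself defective; the text to change is 9.4.

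What the objection does not remove is the omission: two differently sourced groups, a test without covariates, and one named adjustment variable with no method.

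**Conclusion.** The point holds as a gap in 9.4. As written, the comparison cannot separate group from BMI or sex if either is imbalanced and related to the endpoint. Both conditions are needed; without either one the test keeps its nominal level.

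The documents support the mechanism only in principle, through thoracic impedance and tissue conductivity. The sex effect in particular is subject-matter reasoning. Under the assumed BMI gaps of 0.5 to 1.0 SD and correlations of 0.2 to 0.5, the false-positive rate is about 6% to 50%, against about 5% with adjustment. The adjusted figure is a best case, because the simulated model is correctly specified. The range shows sensitivity to the assumptions and is not an estimate for this study. The documents do not show that a bias exists, or which way it would run. The change is worth making because it costs little.

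**What to change.** In 9.4:

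- Make the ROI-share comparison a regression on ranks with group, age, BMI and sex, or a permutation test on residuals from the same covariates. This also supplies the missing method for the age adjustment.
- Record BMI and sex for every participant and tabulate both by group, so that readers can see any imbalance.
- Present the 32x32 pixel comparison as descriptive unless it is adjusted in the same way.

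If volunteers are still being recruited, balancing them to the patients on BMI and sex as well as age would reduce the reliance on the model, which matters with only 20 patients.

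**Cost.** Two more model terms. If BMI and sex are unrelated to the EIT values, adding them to an age-adjusted model lowered simulated power from 78% to 77% with balanced groups, and from 79% to 73% with imbalanced groups. BMI must be retrieved from routine records for the retrospective patients and may be missing for some. For volunteers it has to be recorded at the EIT visit.
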